6.2 SOFTWARE

Analyses will be conducted using SAS Version 9.2 or higher.

6.3 CHANGES TO PLANNED ANALYSES

Draft versions of the SAP will be numbered sequentially as Version 0.0i. The final approved version will be numbered as Version 1.00. Revisions after the “Final” version will be numbered as Version 1.0x. The Clinical Study Report will document any changes made after the final version approved before unblinding.

7.0 DESCRIPTION OF THE STUDY POPULATIONS

All tables, figures, and listings must include a population descriptor (e.g., ITT population, mITT population, safety population, or per protocol population) in the title.

7.1 DISPOSITION

Subject disposition summaries will be presented by treatment arm and will include the number of subjects randomized, the number and percentage of randomized subjects in the safety, ITT, mITT and per protocol (if applicable) populations, as well as the number and percentage of subjects who complete the study. The summaries will also include the reasons for early discontinuation from the study.

Disposition summaries will be presented for safety, ITT, mITT, and per protocol populations (if applicable) separately.

7.2 DEMOGRAPHIC AND BASELINE CHARACTERISTICS

A summary of demographics and baseline characteristics will be presented by treatment arm and overall for the ITT and safety populations. The demographic characteristics will consist of age, sex, ethnicity, and race using descriptive statistics.

Demographic data including age, race, ethnicity, and gender, as well as baseline clinical characteristics will be summarized. Age will be calculated based on the following conditional algorithm:

- Has the patient had his/her birthday this year?
 - Yes, then AGE = (year of informed consent) – (year of birth).
 - No, then AGE = (year of informed consent) – (year of birth) – 1.

Clinical baseline characteristics (including height, weight and body mass index [BMI]), psychosocial history, and substance abuse treatment history will be summarized by treatment group and overall.

7.3 MEDICAL HISTORY

Medical history will be coded using MedDRA dictionary Version 18. Medical history will be presented.

8.0 PRIOR AND CONCOMITANT MEDICATIONS

All medications recorded on the CRFs will be coded using the WHO DRUG Dictionary Enhanced March 2015. Prior and concomitant medications will be summarized by treatment arm in the safety population by anatomical therapeutic chemical Class Level 4 and WHO Drug base substance preferred name.

Prior medications are defined as medications with stop dates occurring before the date of first administration of any study treatment component. Concomitant medications are defined as medications with start dates occurring on or after the date of first administration of any study treatment component and no more than 30 days after the last administration of any study treatment component. Medications

with start and stop dates that bracket the date of first administration of any study treatment component will be summarized as both prior and concomitant medications.

Medications that clearly stopped prior to date of first administration of any study treatment component will be included in the prior medications table, and medications that clearly started on or after date of first administration of any study treatment component will be included in the concomitant medications table. All other medications will be included in both the prior and concomitant medications tables.

Prior and concomitant medication will be summarized for the safety population.

9.0 EFFICACY ANALYSES

9.1 PRIMARY EFFICACY VARIABLE – RESPONDER RATE

The responder definition will be derived based on urine samples obtained from Weeks 10, 11, 12 and 13 in Phase 1 and samples obtained at Weeks 17 (end of Month 1 of Phase 2), 21 (end of Month 2 of Phase 2) and 25 (end of Month 3 of Phase 2) and at the 3 random samples in Phase 2.

To be a responder for Phase 1, the subject must have no evidence of illicit opioids use at Week 13 and have no evidence of illicit opioids use for at least 2 out of the three weeks from Week 10 to Week 12. To be a responder for Phase 2, the subject must have no evidence of illicit opioids use at Month 6 and have no evidence of illicit opioids use in 5 out of the 6 illicit opioids use assessments in Phase 2. To be a responder for the study, the subject must be a responder for both Phases 1 and 2.

Please note that EMA requested percent negative urine samples as the primary endpoint for their evaluation. Percent negative urine samples is the first secondary endpoint (see Section 9.2.1) for this study.

9.1.1 DERIVATION OF RESPONSE RATE

For the purpose of deriving the RR, the following rules will be used:

Time Windows for Illicit Opioid Use Assessment

For easy discussion, unless otherwise stated a window denoted as Week (x+, y) for efficacy assessment is a window that covers a period between Week x +1 day to Week y day (exclusive of Week x day but inclusive of Week y day). A window denoted as Weeks x-y for efficacy assessment is a window that covers a period between Week x day to Week y day (inclusive of Week x day and Week y day).

Subjects will receive 12 weekly injections from Week 1 (Day 1 Week 1) through Week 12. Subjects will then receive three monthly injections at Week 13, Week 17, and Week 21. Since the last weekly dosing will occur at Week 12, the efficacy assessments collected at Week 13 reflected effects of weekly dosing in Phase 1. The Phase 1 window is Week (1+, 13). Since the last monthly dosing will occur at Week 21 Phase 2 efficacy window will be Week (13+, 25).

Due to visit date deviation, the actual days in Phase 1 and Phase 2 may not be exactly equal to 91 days (13 weeks) and 84 days (12 weeks), respectively. Similarly, for analysis purpose, weekly and monthly windows will be based on the visit windows, instead of exact 7-day and exact 30-day windows.

Evidence of Illicit Opioid Use within a Window

Subject response for Phase 1 will be based on the 12 scheduled weekly post-baseline urine samples collected from Weeks 2-13. Subject response for Phase 2 will be based on the 3 scheduled monthly urine samples collected at Weeks 17, 21, and Week 25 and the 3 random samples. Evidence of illicit opioid use within a window is defined as a positive opioid urine toxicology result or self-reported illicit opioid use within that window, including the results from random urine toxicology samples (in Phase 2) obtained within that window. Therefore, there is evidence of illicit opioid use, if self-reported illicit opioid use is present, regardless of the opioid urine toxicology result is positive or negative.

If urine toxicology samples are missing, for example, due to missing scheduled visit, early discontinuation of the study, or subject's refusal to provide the samples (scheduled or random samples), the results will be imputed as positive according to the Missing Value Imputation rules discussed in Section 9.1.3 of the SAP.

9.1.2 PRIMARY ANALYSIS

The primary analysis of RR will be performed based on the ITT population.

An analysis of non-inferiority in the primary efficacy variable between the two treatments arms will be performed using a margin of 10% point.

Non-inferiority will be concluded if the two-sided 95% confidence interval for the difference between the probabilities of response (Active- Control) is above -0.10 . The 95% confidence interval, (LB, UB), will be derived using normal approximation:

$$\text{LB} = (P_T - P_C) - 1.96 * (1/N_T * P_T * (1 - P_T) + 1/N_C * P_C * (1 - P_C))^{0.5}, \text{ and}$$
$$\text{UB} = (P_T - P_C) + 1.96 * (1/N_T * P_T * (1 - P_T) + 1/N_C * P_C * (1 - P_C))^{0.5}, \text{ where}$$

P_T and P_C are observed proportions of the responders for the treatment and the control, respectively, and N_T and N_C are the sample sizes for the treatment and the control, respectively.

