9.3. Method of Assigning Subjects to Treatment Groups

Randomization will be used to avoid bias in the assignment of subjects to treatments, to increase the likelihood that known and unknown subject attributes (e.g., demographics, baseline characteristics) are evenly balanced across treatment groups, and to enhance the validity of statistical comparisons across treatment groups.

Subjects who have provided written informed consent will be assigned a unique number in the screening process. This number will be used to identify the subject throughout the trial.

Subjects who have met the eligibility criteria (Section 8) during the re-check on Day 1 and who have tolerated the 4 mg test dose will be randomized to one of the two treatment groups in a 1:1 ratio (Group 1: Daily SL BPN plus SC placebo injections or Group 2: CAM2038 [q1w and q4w] SC injections plus SL placebo tablets). Due to the size of the trial, it is expected that subjects will be balanced for various other baseline factors, including age.

Once any subject number or randomization number is assigned, it cannot be reassigned to any other subject. This trial will use central randomization, through an Interactive Voice Response System and/or by an Interactive Web Response System managed by the Sponsor.

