3.0 INTRODUCTION

This statistical analysis plan (SAP) is based on Protocol HS-11-421 Amendment 5, dated on November 3, 2016.

The purpose of this document is to provide details on study populations and on how the variables will be derived, how missing data will be handled, as well as details on statistical methodologies to be used to analyze the safety and efficacy data from the study.

The document may evolve over time, for example, to reflect the requirements of protocol amendments or regulatory requests. However, the final SAP must be finalized, approved by the Sponsor, and placed on file before database is locked and treatment codes are unblinded. Deviations from the approved plan will be noted in the clinical study report.

The primary endpoint response rate will be used to address the regulatory requirements as outlined by the US Food and Drug Administration (FDA). Specifically, the FDA requested an alternative primary efficacy responder definition on September 1, 2016, which have been incorporated in this final SAP. Additionally, the FDA provided comments on November 4, 2016 and recommended a NI margin of 10% points to be reasonable NI margin for the study. This change is reflected in this final SAP.

The European Medical Agency (EMA) has requested percent negative urine samples as the primary endpoint and retention rate as key secondary endpoint. These requests are addressed in a separate SAP for EMA submission. The variables related to the percentage of urine sample negative (EMA specific variables) are removed from Version 1.01 that is for FDA submission.

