6.0 GENERAL CONVENTIONS

Unless otherwise stated, all analyses will be performed using SAS Version 9.2 or higher and all hypothesis tests will be conducted at a two-sided significance level of 0.05. P-values will be presented with 3 decimals and p-values that are less than 0.001 will be presented as <0.001.

Continuous (non survival related) data will be summarized using descriptive statistics: number of observations (n), mean, standard deviation (SD), median, minimum, and maximum. Frequencies and percentages will be used to summarize categorical (discrete) data. Presentations of categorical data will generally suppress percentages for items where the count is zero in order to draw attention to the nonzero counts. In general, mean, standard deviation, median, minimum, maximum, and percentages will be presented with one decimal.

Unless otherwise stated, confidence intervals, when presented, will be constructed at the two-sided 95% level. For binomial variables, the 95% confidence intervals will be constructed using the normal approximation without continuity correction.

Data listings will present all data collected on case report forms (CRFs) by study drug, center, and subject number. Unless otherwise stated data will be presented by treatment and overall.

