9.6 POWER AND SAMPLE SIZE JUSTIFICATION

The sample size of approximately 190 per treatment arm (380 total) will provide approximately 82% power to establish the non-inferiority with a 13.5% non-inferiority margin for the primary efficacy variable, RR Weeks 2-25. In the sample size calculation, it was assumed that the proportion of response in both the active treatment arm and control treatment arm is 70%.

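### The primary risk difference uses none of the baseline data scheduled for every subject; adjusting for them is a cheap, modest gain in precision that neither causes nor cures the low power at the 10-point margin

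*SAP*

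**What the plan says.** SAP 9.1.2 takes the observed responder proportion in each arm, subtracts, and attaches an unpooled Wald interval: "The 95% confidence interval, (LB, UB), will be derived using normal approximation". The margin is set in the same section: "An analysis of non-inferiority in the primary efficacy variable between the two treatments arms will be performed using a margin of 10% point". Non-inferiority is concluded if the interval lies above -0.10. The Protocol synopsis and Protocol 12.3.2.1 give the same formula with a 13.5-point margin. No covariate, site or stratification factor enters, and neither document plans an adjusted analysis of response rate, even as support.

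Baseline balance is left to randomization. Protocol 9.3 says: "Due to the size of the trial, it is expected that subjects will be balanced for various other baseline factors, including age". SAP 4.4 repeats this, and no stratification factor is named.

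The pre-treatment data are extensive. Protocol 7.1 and Table 3 schedule a urine sample before the first dose and an illicit-use self-report. Table 3 also places SOWS, COWS and the craving VAS before the Day 1 test dose. Protocol 10.1.2 and 10.1.5 add demographics and a full substance-use and treatment history. The SAP summarizes baseline characteristics (7.2) and uses baseline scores as ANCOVA covariates for exploratory scales (9.3.9, 9.3.10, 9.3.14), but not for the endpoint that decides the trial.

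**The concern.** If some baseline variables predict response, the crude interval is wider than it needs to be, and chance imbalance in those variables stays in the estimate. An adjusted estimator that targets the same marginal risk difference removes part of that noise without changing the estimand, margin or decision rule. Interval width matters here because, at the SAP's margin and under its own assumptions, the chance of success when the arms are truly equal is only a little better than even.

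**Working it through.** **Inputs.** 190 per arm and 70% response in both arms (SAP 9.6). Margin 10 points (SAP 9.1.2), against 13.5 points in the power statement (SAP 9.6). SAP 6.0 states that "all hypothesis tests will be conducted at a two-sided significance level of 0.05", so the lower 95% limit is a one-sided 2.5% test. There is no dropout inflation: missing samples count as positive (SAP 9.1.3), so every randomized subject stays in the denominator.

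**The plan's own figure.** SE = √(2 × 0.7 × 0.3 / 190) = 0.0470. Power = Φ(margin/SE − 1.96).
- At 13.5 points: Φ(2.871 − 1.96) = Φ(0.911) = 81.9%. The stated 82% reproduces; the exact binomial power of the SAP's Wald rule is also 81.9%.
- At 10 points: Φ(2.127 − 1.96) = Φ(0.167) = 56.6% (exact binomial 56.8%).

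**Effect of adjustment.** Replace SE by SE × √(1 − R²), where R² is the share of outcome variance explained by baseline covariates. The documents give no value, so this is an assumed range.

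| R² | Power at 10 points | Gain (points) |
|---|---|---|
| 0 | 56.6% | 0 |
| 0.02 | 57.5% | 0.9 |
| 0.05 | 58.8% | 2.2 |
| 0.10 | 61.1% | 4.5 |
| 0.15 | 63.6% | 7.0 |

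An R² of 0.10 is worth 1/(1 − 0.10) = 1.11, or about 11% more subjects.

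**Simulation of the estimator.** A standardized logistic risk difference with an influence-function SE and one normally distributed covariate was run 3,000 times at 190 per arm and 70% response in both arms.
- R² 0: 55.3% crude, 55.7% adjusted, so nothing is lost.
- R² 0.05: 57.5% to 58.8%.
- R² 0.10: 57.8% to 60.7%.
- R² 0.16: 56.7% to 62.8%.

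These gains (1.3, 2.9 and 6.1 points) are somewhat smaller than the formula gives. One-sided type I error at a true difference of -10 points (nominal 2.5%) was 2.0% crude and 2.3% adjusted at R² 0.16, and 2.9% and 3.0% at R² 0. The Monte Carlo standard error is √(0.025 × 0.975/3000), about 0.3 points, so none of these is a clear departure from nominal.

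**What would restore 80% power.**
- By sample size: 2 × 0.21 × (1.96 + 0.8416)² / 0.10² = 330 per arm.
- By adjustment alone: R² = 1 − (0.10/2.8016)² / (0.42/190) = 0.42.

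**Dependence on the response rate.** Crude power at 10 points is 49.6% at a 50% rate, and 54.5% at the 33% rate that Protocol 12.5 cites for sublingual buprenorphine/naloxone in an earlier trial.

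**The case against.** A pre-specified two-proportion comparison in a randomized ITT population is valid, and expecting balance with 380 subjects is reasonable. Both points stand. A reader might infer from the missing covariates that the primary analysis is biased or in error; the documents do not support that.

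A reader might also infer that leaving out covariates explains the 57% power, or that adding them would repair it. Neither follows. SAP 3.0 records that the regulator "recommended a NI margin of 10% points to be reasonable NI margin for the study". The test adopted that margin, but SAP 9.6 still says the sample "will provide approximately 82% power to establish the non-inferiority with a 13.5% non-inferiority margin". The shortfall comes from that change, and under every R² in the table the trial stays well below 80%.

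The benefit rests wholly on an assumed R². The simulation favours adjustment, because it used a single, correctly modelled covariate. The obvious candidates may also be weak. Protocol 8.1 enrols treatment-seeking subjects with moderate or severe disorder and no medication-assisted treatment for 60 days, so Day 1 opioid urine may be nearly always positive. Subjects are told to arrive in mild withdrawal (Protocol 7.1.2), which may compress the craving scores. This limits the expected gain, but the R² 0 simulation shows that little is lost if the covariates prove useless.

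Adjustment is cheap but not free. SAP 9.1.3 leaves other missing values unimputed, so a logistic model would drop ITT subjects with a missing covariate. SAP 6.1 defines baseline both as the last observation and as an average of several. Revising the primary estimator reopens a SAP that already incorporates regulatory comments. These objections shape the fix but do not defeat it.

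**Conclusion.** The point holds as an efficiency weakness. The primary analysis leaves unused the baseline data that the protocol schedules for everyone. Under 70% response in both arms, 190 per arm and a 10-point margin, adjustment would lift power from 56.6% to about 57.5% to 63.6% for an assumed R² of 0.02 to 0.15. Simulated gains at the lower R² values are somewhat smaller, and the true gain could be near zero. The low power itself is a separate matter of margin and sample size that SAP 9.6 should acknowledge.

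**What to change.** Before unblinding, amend SAP 9.1.2 as follows:
- **Estimator.** Make the primary estimate a standardized (g-computation) marginal risk difference from a logistic model with treatment and one fixed, short list of baseline covariates that are likely to vary. An example is Desire to Use VAS before the test dose, baseline frequency of self-reported use, age and sex. Add Day 1 urine only if blinded pooled data show that it varies.
- **Variance.** Name one method. The influence-function standard error used in the simulation is suitable.
- **Baseline.** Define it for these covariates as the last pre-dose value.
- **Missing covariates.** Add a simple rule, such as imputing the overall mean without regard to treatment, so that all ITT subjects stay in the model.
- **Decision rule.** Leave it unchanged: lower 95% limit above -0.10. Keep the crude Wald interval as a sensitivity analysis.

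The Protocol synopsis and 12.3.2.1 carry the crude formula. Protocol 12.1 allows the SAP to amend the listed analyses, so the SAP should record the departure. Separately, SAP 9.6 should state that power at the 10-point margin is about 57% under its own assumptions.

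The cost is SAP text and standard code, with no new data, visits or subjects. The downside is a slightly more complex primary analysis and a further revision of a SAP that already incorporates FDA comments. SAP 3.0 permits revision until database lock and unblinding.

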9.1.3 MISSING VALUE IMPUTATION

Unless otherwise stated the following procedures will be used to handle missing values for urine toxicology.

All missing urine toxicology samples (scheduled or random samples), regardless of reasons, will be imputed as positive.

Unless otherwise stated all other missing values will not be imputed.

9.2 SECONDARY EFFICACY VARIABLES

Secondary efficacy variables will include:

- Cumulative Distribution Function (CDF) of percent urine samples negative for illicit opioids (supported by self-reported illicit opioids use results) based on Weeks 5-25;

- Time to sustained abstinence of opioid use (supported by self-reported illicit opioids use results);
- Percent of subjects remaining in the study (retention rate);

9.2.1 CUMULATIVE DISTRIBUTION FUNCTION (CDF) OF PERCENT SAMPLES THAT ARE NEGATIVE FOR ILLICIT OPIOIDS (WEEKS 5-25)

Percent negative samples from 15 samples (9 weekly assessments obtained from Weeks 5 to 13, plus 3 monthly assessments obtained at Weeks 17, 21, and 25 and plus 3 random samples) will be calculated for each subject. Missing samples will be imputed as positive before the percentage is derived.

The null hypothesis of no difference in the CDF of the percent of urine samples that are negative for illicit opioids over Weeks 5-25 will be tested at the 5% significance level using Wilcoxon Rank-Sum test. The empirical CDF plot will be presented.

9.2.2 TIME TO SUSTAINED ABSTINENCE OF OPIOID USE

For the purpose of deriving time to sustained abstinence of opioid use (i.e., no opioid use through the rest of treatment period for at least two months), the time will be defined as:

- If the sustained abstinence is obtained during the scheduled visit, time is the number of days between randomization day to the scheduled visit day. For example, if first sustained abstinence is obtained at the Week 8 visit, the time would be 56.
- If the first sustained abstinence is obtained during a random test, time is the number of days between randomization day to the day that random sample is obtained (Random Sample Date – Randomization Date).

The same definition for evidence of illicit opioid use (see Section 9.1.1) and the same rules for missing value imputation (see Section 9.1.3) will be used in the calculation.

Time to sustained abstinence of opioid use will be analyzed via a log-rank model with treatment effects. Time to event “Survival” curve will be presented using Kaplan-Meier method. Median time to event and the 95% confidence interval of the median times will be presented, if estimable. In this time to event analyses, subjects who do not have any opioid-positive results during the entire study and who do not have any opioid-positive results before discontinuing from the study will be censored at Day 175 (Week 25 day), the day when the last sample will be obtained.

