7. INVESTIGATIONAL PLAN

7.1. Overall Trial Design and Plan

This is a randomized, double-blind, double-dummy, active-controlled, parallel group multi-center trial, designed to evaluate the non-inferiority of CAM2038 compared to an existing standard of care (SL BPN) in initiation and maintenance treatment with BPN. The trial will involve 4 phases: Screening, Phase 1 (weekly visits), Phase 2 (monthly visits), and Follow-up.

Following Screening and confirmation of eligibility, subjects will be randomized to one of two treatment groups in a 1:1 ratio:

- Group 1: SL BPN tablets + placebo SC injections
- Group 2: CAM2038 SC injections + SL placebo tablets

Following randomization, subjects will undergo initiation of BPN with either SL BPN or SC CAM2038 q1w and participate in weekly visits for 12 weeks (Phase 1). After Week 12, subjects will be transitioned to Phase 2 with monthly visits. During Phase 2, subjects in Group 1 will continue treatment with monthly dispensing of daily SL BPN treatment and monthly placebo SC injections, and subjects in Group 2 (receiving CAM2038 q1w) will be transferred to monthly injections of CAM2038 q4w and monthly dispensing of daily SL placebo. Subjects will participate in up to 6 visits during the 12 weeks of Phase 2; 3 scheduled monthly visits and 3 random urine toxicology visits. At each visit, efficacy and safety outcome measures will be assessed. After Phase 2, the subjects will be followed-up for 1 month.

A total of 20 opioid urine toxicology samples will be collected during the study:

- 1 sample at Screening
- 1 sample at baseline (Day 1/Week 1) before first dose of CAM2038 q1w
- 12 samples will be collected at the scheduled 12 weekly visits of Phase 1 (Week 2 to Week 13 [i.e. 1 week after the last CAM2038 q1w treatment])
- 6 samples will be collected during the 12 weeks of Phase 2
 - 3 at the scheduled monthly visits (Weeks 17, 21 and 25)
 - 3 at random urine toxicology visits (taken during the period from Week 13 to Week 25).

A self-report of drug use will accompany every urine toxicology test as outlined in Table 3 and Table 4. Each subject will participate in the trial for up to 31 weeks, including up to 24 weeks of treatment with SL BPN or CAM2038. Subjects who complete the 24 weeks of treatment will be transitioned to standard of care (e.g., SL BPN) and be followed up for 4 weeks.

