Day 4: All subjects will return to the clinic on Day 4 and will receive a single CAM2038 q1w 8 mg or Placebo SC injection (0.16 mL of active or placebo). In situations where the visit cannot occur on Day 4 due to logistical constraints, the visit may occur one day early or one day late (+/- 1 day). However, it is strongly encouraged to have the subject return on Day 4.

[figure not shown]
All subjects will continue with the 16 mg SL BPN/Placebo (two 8mg SL BPN or placebo tablets per day). This may be observed in the clinic or be taken at home.

Subjects will be provided with adequate amount of SL BPN/Placebo tablets for take-home to last through Day 7.

Days 5 to 7: All subjects will be allowed to return to the clinic through an Unscheduled Visit, if continued withdrawal symptoms are present. During Days 5 to 7, one additional SC injection (CAM2038 q1w 8 mg or Placebo – not to exceed total weekly dose of CAM2038 q1w 32mg or placebo) and increase in SL BPN/Placebo dose may be provided (not to exceed 24 mg SL BPN/Placebo per day).

Additional outcomes measures and procedures to be performed at each visit are outlined in Table 3.

Week 1 CLINIC VISIT FLOW CHART

Day 2

- All subjects will return on Day 2 for observations on tolerability/safety and observed dosing for SL BPN/Placebo (16 mg SL BPN/Placebo).
- Subjects will be provided take home dose of 16 mg SL BPN/Placebo for Day 3.

Day 4

- All subjects return to the clinic on Day 4 for an additional CAM2038 q1w 8 mg SC or Placebo SC injection.
- All subjects will receive 16 mg SL BPN/Placebo daily to take home for Days 4-7 (Day 4 can be taken in the clinic or be taken at home).

Day 5-7

- All subjects will be instructed to return to the clinic if their withdrawal symptoms are not adequately controlled. Subjects that are not adequately controlled should receive additional SL BPN/Placebo (not to exceed 24 mg or 3 tabs/day) and one additional CAM2038 q1w 8 mg or placebo SC injection.

Figure 4 Overview of Induction Procedures

BPN=buprenorphine; SC=subcutaneous; SL=sublingual

On Day 2, subjects will be provided with SL tablets and instructions for dosing. The daily SL BPN/Placebo dose for Days 2-4 will be 16 mg and the maximum daily SL BPN/Placebo dose for Days 5-7 will be 24 mg.

Weeks 2 to 12:

Day 8 (Week 2): All subjects will return to the clinic on Day 8.

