9. TREATMENTS

9.1. Treatment Administration

All trial drugs will be administered in a double-blind, double-dummy manner, such that subjects will receive both SL tablets (active BPN or Placebo) and SC injections (active CAM2038 q1w/CAM2038 q4w or Placebo) throughout the trial. Subjects will receive treatment for up to 24 weeks during the trial; 12 weeks during Phase 1 and 12 weeks during Phase 2.

CAM2038/Placebo will be injected in the buttocks, abdomen, thighs and the upper back of the arms and the injection sites will be rotated such that no injections are administered into the same site. A total of 26 sites have been identified and a pictorial of potential injection sites will be provided in the trial Manual of Procedures (MOP). The following rules apply:

- CAM2038 q1w/Placebo must not be administered into a previously injected site for at least 8 weeks.
- CAM2038 q4w/Placebo must not be administered in a site previously injected with CAM2038 q4w/Placebo.

The Investigator will keep record of the injection site at each treatment visit.

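### The worked example for time to sustained abstinence (Week 8 = 56 days) contradicts its own rule, which gives 49 days; if programmed, it puts scheduled-visit events 7 days later than random-test events (minor)

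*SAP*

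**What the plan says.** For an event at a scheduled visit, SAP 9.2.2 states that "time is the number of days between randomization day to the scheduled visit day". It adds the illustration "For example, if first sustained abstinence is obtained at the Week 8 visit, the time would be 56". For an event at a random test, "time is the number of days between randomization day to the day that random sample is obtained", which the SAP spells out as one calendar date minus the other. Certain subjects "will be censored at Day 175 (Week 25 day), the day when the last sample will be obtained". Protocol 12.3.2.4 carries the same rules, the same example and the same Day 175.

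SAP 9.1.1 says that the actual lengths of Phases 1 and 2 "may not be exactly equal to 91 days (13 weeks) and 84 days (12 weeks), respectively".

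The calendar is set elsewhere. Protocol 7.1 lists "1 sample at baseline (Day 1/Week 1) before first dose of CAM2038 q1w", and Protocol 7.1.2 and 10.2 place randomization on Day 1. Protocol 7.1.2 continues: "Day 8 (Week 2): All subjects will return to the clinic on Day 8". Protocol 9.1 gives the durations: "Subjects will receive treatment for up to 24 weeks during the trial; 12 weeks during Phase 1 and 12 weeks during Phase 2".

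**The concern.** The rule and its example give different answers for the same visit. One programmer who follows the rule sentence gets about 49 for Week 8. Another who follows the example, and sees it supported by Day 175 and 91 days, gets 56. The second dataset holds two clocks in one Kaplan-Meier curve: scheduled-visit events a week late, random-test events on true time.

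The endpoint is secondary and stands third in the ordered testing list of SAP 9.5. What is at stake is whether its derivation can be reproduced and whether the reported times are right.

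**Working it through.** **Inputs.** Randomization is on Day 1, which is in Week 1 (Protocol 7.1, 7.1.2, 10.2; SAP 9.1.1). The Week 2 visit is Day 8, and visits fall at the start of the week (Protocol 7.1.2). The window is ±2 days for Weeks 2 to 13 and ±7 days for the later monthly visits (Protocol Tables 3 and 4). Treatment lasts 12 + 12 weeks (Protocol 9.1).

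**Step 1: reproduce the plan's figures.** Multiplying 7 by the week number gives all three: 7 × 8 = 56, 7 × 13 = 91, 7 × 25 = 175. Also 91 + 84 = 175. This is one convention applied throughout, not an isolated slip.

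**Step 2: apply the documents' calendar.** The study day of the Week n visit is 7(n − 1) + 1. Elapsed days from randomization are 7(n − 1).

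| Visit | Study day | Elapsed days | 7 × week | Excess over elapsed |
|---|---|---|---|---|
| Week 2 | 8 | 7 | 14 | 7 |
| Week 8 | 50 | 49 | 56 | 7 |
| Week 13 | 85 | 84 | 91 | 7 |
| Week 17 | 113 | 112 | 119 | 7 |
| Week 25 | 169 | 168 | 175 | 7 |

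**Step 3: look for another reading that gives 56.** Elapsed time gives 49 and inclusive study day gives 50. The ±2-day window gives 49 − 2 = 47 to 49 + 2 = 51 elapsed days. None reaches 56.

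**Step 4: cross-check the calendar.** Twelve weeks are 12 × 7 = 84 days and 24 weeks are 168 days, matching the elapsed times for Weeks 13 and 25. Total participation of up to 31 weeks (Protocol 7.1) is 3 weeks of screening plus 28 weeks from Week 1 to Week 29; the other convention gives 3 + 29 = 32. SAP 9.3.6 starts the period after two months of treatment at Week 9, which is 7 × 8 = 56 elapsed days. So 56 belongs to Week 9.

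**Step 5: which events could change order.** The definition requires at least two months of abstinence to the end of treatment. Taking two months as 56 days (an assumption, consistent with SAP 9.3.6), the last nominal event time is 168 − 56 = 112 days.

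- Week 13: true 84, coded 91. Random tests on days 85 to 90 are later in truth but would rank earlier. The order is reversed.
- Week 17: true 112, coded 119. A reversal needs a random test on days 113 to 118, leaving 168 − 113 = 55 down to 168 − 118 = 50 days. Nominally these are not events.

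**Step 6: size of the effect, by illustration.** A simulation of 300 trials assumed 190 per arm, 65% reaching the event, and per-visit onset probabilities of 0.09 and 0.11 in the two arms. Of the events with onset after Week 13, 60% were timed at random tests on days 85 to 111 and the rest at Week 17. Recoding scheduled visits by +7 days changed the 600 arm medians by −3 to +7 days: 99 moved by +7, 324 by 0, and the other 177 by amounts in between. These frequencies reflect the assumed onset pattern and are not a forecast. The log-rank z statistic changed by at most 0.06.

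**The case against.** The strongest reply is that the operative sentence is right. It defines the same kind of date difference as the random-test rule; only an illustration is off. Followed as written, the rule has one clock and no bias. This stands, and it makes every consequence conditional. It does not remove the contradiction, because the example, Day 175 and 91 days all point a programmer the other way.

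Two of the figures also have little force. The 91 days is descriptive, since SAP 9.1.1 bases its windows on visits rather than exact day counts. Censoring at 168 or 175 gives the same Kaplan-Meier estimates and log-rank test if no event can occur after day 112 (119 as coded), and Day 175 lies within the ±7-day window for Week 25. Both replies stand; these corrections are for consistency.

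A reader might infer more than the documents support:

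- **That the test of hypothesis 3 is at risk.** The shift is common to both arms and the log-rank test uses only order. Nominally, order changes only for Week 13 against random tests in the following six days.
- **That reversals also occur around Week 17.** On the nominal schedule such random tests leave less than 56 days. Only a late Week 25 visit could make one an event.
- **That every reported median is a week too long.** This requires a median that is estimable and falls at a scheduled visit. With missing samples counted as positive (SAP 9.1.3), estimability is uncertain.

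**Conclusion.** The inconsistency is definite: 56 stated against 49 by the rule, an excess of 7 days (7/49 = 14%), with the same offset behind Day 175 and 91 days. It rests only on Week 1 = Day 1 = randomization and Week 2 = Day 8, both stated in the documents.

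The consequence is conditional on programming the example or its convention. It would then be a 7-day overstatement of any estimable median at a scheduled visit, in either arm, and some misordering just after Week 13. The statement that the log-rank effect is negligible rests on the common shift and on the illustrative simulation. This is a defect of time scale and reporting, with no material threat to type I error or power. Severity is minor.

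**What to change.** In SAP 9.2.2, state one rule for all events: actual sample collection date minus randomization date. Change the worked example to 49 days for a Week 8 visit on its nominal day. Put the Week 25 censoring time on the same scale, as 168 elapsed days (study Day 169) or the actual date. In SAP 9.1.1, change the Phase 1 length to 84 days (12 weeks) for consistency.

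The cost is a few words in the SAP before database lock and unblinding. No new data are needed, since the existing rules already rely on visit and sample dates. Protocol 12.1 leaves analysis detail to the SAP, so Protocol 12.3.2.4 can be aligned at the next amendment; a separate amendment, with the signatures and possible IRB review under Protocol 13.6, is not warranted for this alone.
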